## 7.3 **DISPOSITION OF SUBJECTS**

A summary of screened subjects will display the number of subjects screened and the number of subjects in the Total Set, FAS, SAF and PPS; overall and at each center. Reason for exclusion from each analysis population will also be presented.

Subject disposition will be summarized for the Total Set and will include the frequency and percentage of subjects who completed each visit, the frequency and percentage of subjects who were screen failures, the frequency and percentage of subjects who discontinued prematurely from the study along with the frequency and percentage of subjects for each reason for screen failure/discontinuation. This information will be displayed by treatment.

The primary reason for screen failure should be recorded using the following categories:

- 1. Pretreatment event (PTE) or adverse event (AE),
- 2. Did not meet inclusion criteria or did meet exclusion criteria.
- 3. Significant protocol deviation.
- 4. Lost to follow-up.
- 5. Voluntary withdrawal (specify reason).
- 6. Study termination.
- 7. Other (specify reason).

The primary reason for discontinuation should be recorded using the following categories:

- 1. PTE or AE, including liver function test (LFT) abnormalities.
- 2. Significant protocol deviation.
- 3. Lost to follow-up.
- 4. Voluntary withdrawal.
- 5. Study termination.
- 6. Pregnancy.
- 7. Lack of efficacy.
- 8. Unblinding of subject treatment.
- 9. Other.

Significant protocol deviations for the FAS will be summarized according to the category of deviation, by site and treatment group.

CROSS-REGIONAL TEMPLATE				
Template Number:	C-TMPL-DO-801	Page:	16 of 31	
Version Number:	1.2	Effective Date:	14 Sep 2015	
This version replaces:	1.1			
Parent Document:	C-SOP-DO-800			
Template Title: St	tatistical Analysis Plan (Legacy Takeda)			

#### 7.4 DEMOGRAPHIC AND BASELINE CHARACTERISTICS

Demographic and baseline characteristics will include age (years) at date of informed consent, race, ethnicity, smoking status, gender, height (cm), weight (kg) at Screening, body mass index (BMI) (kg/m2) at Screening.

Demographic and baseline characteristics will be summarized by randomised treatment group and total for the Total Set. Subjects in the Total Set who were screen failures will be included in a 'Screen Fail' group for presentation purposes and included in the total column.

## 7.5 MEDICAL HISTORY AND CONCURRENT MEDICAL CONDITIONS

Any significant relevant illness that was resolved before screening will be recorded as medical history. Any relevant illness that is present at the day of the screening visit will be documented as concomitant illness. Medical histories and concomitant illnesses will be coded according to the Medical Dictionary for Regulatory Activities (MedDRA), current version. Medical histories and concomitant illnesses will be summarized separately, by system organ class (SOC) and preferred term (PT). Frequencies and percentages will be displayed by treatment and in total.

## 7.6 MEDICATION HISTORY AND CONCOMITANT MEDICATIONS

Medication history information includes any medication relevant to eligibility criteria and efficacy/safety evaluation stopped at or within 1 month prior to signing of informed consent.

Concomitant medication is any medication other than the IMP that is administered during the trial including screening. Concomitant medications will be coded using the World Health Organization Drug Dictionary (WHODrug). Concomitant medications and medication history will be summarized separately for the SAF as the frequency and percentage of patients taking each medication. If a patient took a particular coded medication more than once, the patient will be counted only once for that medication total. If a patient took more than one medication in a particular therapeutic class, the patient will be counted only once in that therapeutic class total.

A total of 10 mg of bisacodyl suppository (or an equivalent drug) may be prescribed as a standard rescue medication if a subject has no adequate BM for 3 consecutive days during the study. When bisacodyl suppository does not improve constipation, glycerin enema (or equivalent drug) may be given. Rescue treatment will be summarized for the FAS by the frequency and percentage of patients for each applied type and time to active rescue treatment.

CROSS-REGIONAL TEMPLATE				
Template Number:	C-TMPL-DO-801	Page:	17 of 31	
Version Number:	1.2	Effective Date:	14 Sep 2015	
This version replaces:	1.1			
Parent Document:	C-SOP-DO-800			
Template Title: S	tatistical Analysis Plan (Legacy Takeda)			

# 7.7 STUDY DRUG EXPOSURE AND COMPLIANCE

Study drug exposure and compliance will be summarized by randomised treatment group for the SAF and FAS respectively. No inferential statistics will be presented. Subject diary compliance will be presented summarized by randomised treatment group and total for the FAS for both screening and double blind periods separately.

Duration of exposure to drug (days) will be calculated as the number of days from the date of first dose to the date of last dose of study drug inclusive. So that exposure = date of last dose-date of first dose + 1. Exposure will be summarised as a continuous variable. Doses taken after Day 28 will be included in the calculation of compliance, as specified compliance is calculated up to the date of the last dose taken,

Study drug is dispensed to subjects on Day -1 only. Subjects are supplied with a bottle containing enough drug for 28 days + 2 extra days. Subjects will be required to bring their study drug bottle with them for each visit of the double blind treatment period; Day 8 (visit 3), Day 15(visit 4) and Day 29 (visit 5). Subjects also record their daily medication intake in their diary.

Study drug compliance will be calculated by:

$$100 \times \left(\frac{\text{number of capsules taken}}{\text{number of capsules expected to be taken}}\right)$$

Overall compliance calculation is considered to indicate compliance with the dosing regimen rather than dosing duration, e.g. if a subject takes all expected doses whilst in the study but withdraws early then compliance will be considered 100%.

Overall compliance will be calculated using:

The number of capsules taken is defined as the difference between the total number of capsules dispensed and the total number of capsules remaining at the last visit.

The number of capsules expected to be taken is defined as the number of capsules prescribed per day (BID dosing) multiplied by the number of days from Day 1 to the date of last dose (last dose date – Day 1 date). If the last dose was a morning dose then this will be increased by 1, if the last dose was an evening dose then this number will be increased by 2. This is to account for the fact that the subject may stop dosing in the morning or evening of the last dose date.

Week 1 compliance will be calculated using:

CROSS-REGIONAL TEMPLATE				
Template Number:	C-TMPL-DO-801	Page:	18 of 31	
Version Number:	1.2	Effective Date:	14 Sep 2015	
This version replaces	: 1.1			
Parent Document:	C-SOP-DO-800			
Template Title:	Statistical Analysis Plan (Legacy Takeda)	1		

The number of capsules taken is derived from the subject diary and will be calculated as the number of completed dosing entries in the diary for the first 7 days following randomization (i.e. Day 1 to Day 7 inclusive). This should be 2 per day, a morning and evening dosing record).

The number of expected capsules to be taken will be calculated as 14 (7 days of BID dosing) if the subject has not withdrawn prior to completing 7 days of dosing. If the subject has withdrawn early (less than 7 days on treatment) then this number will be calculated as for overall compliance.

Overall study drug compliance should also be calculated from the subject's diary, where the number of tablets taken is derived from the number of completed entries (there should be 2 per day, a morning and evening record). The number of expected capsules is calculated as before. If there is a discrepancy between calculated compliance values then unless there is a recorded comment explaining the discrepancy and indicating that the diary value is correct (e.g. a comment may have been recorded indicating that some tablets were lost) the overall compliance calculated using capsule counts will be taken as the correct value.

Study drug compliance will be summarized, for overall compliance and for compliance during Week 1, as a continuous variable and additionally, as a categorical variable, with the following categories:

- Compliance < 70%
- Compliance  $\geq$  70% and < 90%
- Compliance  $\geq$  90% and < 110%
- Compliance >110%

Compliance with the diary will also be assessed. During the double blind period there should be 2 records of study drug intake per day, note that if a dose was missed then 'Not taken' should be ticked, therefore there should be 2 entries per day, regardless of actual doses taken. Also for each day there are two questions requiring an answer (Yes/No): "Did you have bowel movement today?" and "Did you use rescue medication today?" A diary shall be considered compliant for that day if all expected entries for that day are recorded. At a minimum this will mean both questions have been answered and two drug accountability records (either time or 'Not taken'). If 'Yes' has been answered to any question then at least one related entry should be present for that day, with all expected data fields completed. Compliance during the screening period will be similar, except that no study drug intake is recorded and bowel movement is captured either as 'I did not have a bowel movement today" ticked or at least one completed bowel movement record. Subject Diaries are dispensed on Day -15 (visit 1) Day -1, Day 8 and Day 15. Diary compliance checks are conducted at each visit, except screening and follow-up. Diary compliance should be calculated as:

CROSS-REGIONAL TEMPLATE				
Template Number:	C-TMPL-DO-801	Page:	19 of 31	
Version Number:	1.2	Effective Date:	14 Sep 2015	
This version replaces	s: 1.1			
Parent Document:	C-SOP-DO-800			
Template Title:	Statistical Analysis Plan (Legacy Takeda)			

 $100 \times \left(\frac{\text{number of days completed}}{\text{number of days expected to be completed}}\right)$ 

Subject diary compliance will be summarized, for overall compliance during the double blind period and Week 1, as a continuous variable and additionally, as a categorical variable, with the following categories:

- Compliance < 70%
- Compliance  $\geq$  70% and < 80%
- Compliance  $\geq$  80% and < 90%
- Compliance  $\geq$  90% and < 100%
- Compliance = 100%

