# 7.7 Procedure for Reduction of Study Drug Dose Due to Adverse Events

If a subject experiences an adverse event during the Double-Blind Treatment Period, the investigator may decide to reduce the dose or discontinue treatment as needed based on the type and severity of the adverse event.

For a dose reduction, either the morning (with breakfast) or evening (with dinner) dose is discontinued. As a general rule, the investigational drug blind shall not be broken by the investigator, even when the dose in a subject is reduced.

If the report of an adverse event from a subject calls for dose reduction at a point other than the scheduled visit, the investigator determines whether to reduce the dose in the subject. If dose reduction is determined necessary, the investigator must instruct the subject how to reduce the dose.

If the dose is reduced or treatment discontinued in a subject, the reason for dose reduction or discontinuation as well as relevant details should be recorded in the eCRF of the subject. The lubiprostone dose cannot be increased after reduction.

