## Appendix A Schedule of Study Procedures

	Screening	Randomization  Day -1 (a)	Treatment			Follow-up Period	
Study Day/Week	Day -15		First Dose Day 1 (b)	Week 1	Week 2	Final Visit or Early Termination Visit Week 4 (c)	Follow-up Phone Contact Week 6 (0)
Visit Windows (Days): (+/- 2 days)	-15 to -1	-1	1	8	15	29	43
Visit Number:	1	2	N/A	3	4	5	N/A
Informed consent	X						
Demographics and medical history (d)	X						
Inclusion/exclusion criteria (e)	X	X					
Medication history	X						
Physical examination	X					X	
Vital signs (f)	X	X				X	
Weight and height (g)	X					X	
Concomitant medications	X	X	X	X	X	X	X
Concurrent medical conditions	X						
Clinical laboratory tests (h)	X					X	
Pregnancy test (i)	X	X				X	
Urine drug screen	X						
Access IWRS for Subject ID/MED ID/Subject Status	X	X				X	
Dispense investigational drug		X					
Distribute rescue medications prescription as necessary	X	X		X	X		
Drug return/accountability/compliance				X	X	X	
Dispense study diary	X	X		X	X		
Efficacy:		ı				ı	I
Abdominal symptom assessment review (by diary)		X		X	X	X	
PAC-QOL		X			X	X	
Use of rescue medication (by diary)		X		X	X	X	
Diary-keeping by subjects (j)	X	X	X	X	X	X	
Diary collection/ compliance check (k)		X		X	X	X	
Safety:	 						
Guidance on avoidance of pregnancy and ova donation	X	X		X	X	X	
Pretreatment adverse events (1)	X	X					
Adverse events (m)			X	X	X	X	X
Dose reduction (optional) (n)				X	X		
Phone interview							X
	 			 	 		

Footnotes are on last table page.

N/A= not applicable.

- (a) Subjects will be randomized on Day -1, the last day of the Screening Period. They will also receive their bottle of dispensed investigational study drug on Day -1, although they will be instructed to take the first dose the next day, on Day 1.
- (b) Day 1 is the first day of study drug administration. Subjects are to take 1 capsule of lubiprostone 24 μg or placebo with 240 mL of water in the morning with breakfast, and again in the evening with dinner. Repeat this regimen for 4 weeks.
- (c) Conduct Final Visit procedures for subjects discontinued early per Section 7.6. Subjects who withdraw prematurely should return within 1 week of discontinuation for an Early Termination Visit.

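### SAP 7.7 counts two expected capsules a day even after a permitted reduction to one, so overall capsule-count compliance is understated for dose-reduced subjects

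*SAP*

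**What the plan says.** SAP 7.7 states the purpose of the measure: "Overall compliance calculation is considered to indicate compliance with the dosing regimen rather than dosing duration". For overall compliance the numerator is "the difference between the total number of capsules dispensed and the total number of capsules remaining at the last visit". The denominator is "the number of capsules prescribed per day (BID dosing) multiplied by the number of days from Day 1 to the date of last dose", with a last-day adjustment: "If the last dose was a morning dose then this will be increased by 1", and "if the last dose was an evening dose then this number will be increased by 2". For Week 1, "The number of expected capsules to be taken will be calculated as 14 (7 days of BID dosing) if the subject has not withdrawn" early. Overall compliance is also calculated from the diary, but where the two differ the capsule count prevails unless a recorded comment supports the diary. Results are summarised by randomised arm in the FAS, as a continuous value and in four bands, the lowest being under 70%.

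One capsule a day is a permitted regimen. Protocol 7.7, on adverse events, says: "For a dose reduction, either the morning (with breakfast) or evening (with dinner) dose is discontinued". It bars any later increase. Protocol 6.1 also allows blinded reduction at the investigator's discretion, having regard to bowel movement frequency and consistency. SAP 7.7 does not mention dose reduction, although SAP 7.2 (per-protocol set) and SAP 7.8.1 (sensitivity analyses) both deal with it.

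**The concern.** The formula does not do what SAP 7.7 says it is for. If compliance is meant to describe adherence to the regimen, the denominator has to be the regimen the subject was told to follow. Early withdrawal is accommodated and a permitted reduction is not. After a reduction, each capsule withdrawn on the investigator's instruction is counted as a missed dose.

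What is at stake is how the compliance table reads. It would mix investigator-ordered reductions with doses that subjects failed to take, and a reader could not separate the two. If reductions were more frequent in one arm, that arm would appear less adherent for a reason unrelated to adherence.

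**Working it through.** **Inputs.** Two capsules a day, reducible to one (Protocol 7.7 and Table 8.a). A 28-day treatment period (Protocol 6.1). One 60-capsule bottle per subject (Protocol 8.1.1). Numerator, denominator and bands from SAP 7.7. Appendix A lists dose reduction at the Day 8 and Day 15 visits, and Protocol 7.7 also allows it between visits.

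**The plan's own figures.** Week 1 expected capsules: 7 × 2 = 14, as stated. A full course ending with an evening dose: 2 × (28 − 1) + 2 = 56. The SAP's principle that an adherent early withdrawal scores 100% also reproduces: last dose on the evening of Day 10 gives 20 / (2 × 9 + 2) = 100%.

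**A reduced subject.** Let d be the first day on one capsule. Assume dosing continues to Day 28 and no capsule is missed or lost.

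- Taken = 2(d − 1) + (29 − d) = 27 + d.
- Expected under SAP 7.7 = 2 × 27 + 2 = 56 if the evening capsule is kept, or 2 × 27 + 1 = 55 if the morning capsule is kept.
- Expected under the regimen in force = 2(d − 1) + (29 − d), the same as the number taken, so compliance is 100%.

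For d = 8, the bottle comes back with 60 − 35 = 25 capsules, so 35 are counted as taken.

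| First day on one capsule | Taken | Evening kept (of 56) | Morning kept (of 55) | Regimen in force |
|---|---|---|---|---|
| Day 8 | 35 | 62.5% | 63.6% | 100% |
| Day 11 | 38 | 67.9% | 69.1% | 100% |
| Day 12 | 39 | 69.6% | 70.9% | 100% |
| Day 15 | 42 | 75.0% | 76.4% | 100% |
| Day 22 | 49 | 87.5% | 89.1% | 100% |
| Day 23 | 50 | 89.3% | 90.9% | 100% |
| Day 24 | 51 | 91.1% | 92.7% | 100% |

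The SAP value is below 70% for reductions starting by Day 11 (Day 12 if the morning capsule is dropped). It is below 90% for those starting by Day 22 (Day 23 if the morning capsule is dropped). Later reductions stay in the 90 to under 110% band.

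**Diary-based values.** SAP 7.7 counts completed dosing entries, and its diary-compliance text expects two entries a day whether or not the doses were taken. Take a reduction from Day 4. Actual capsules taken in Week 1 are 2 × 3 + 4 = 10. If entries recording an untaken dose are excluded, Week 1 compliance is 10/14 = 71.4%. If they are counted, it is 14/14 = 100%. The direction of the Week 1 error therefore depends on an unsettled numerator. Correcting only the denominator could give 14/10 = 140%.

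The overall diary value has the same ambiguity. For a reduction from Day 8 with the evening capsule kept, it could read 56/56 = 100% against 62.5% by capsule count, and the default rule would select the capsule count.

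**The case against.** The best textual defence is that expected capsules are tied to the number prescribed per day, which could be read as following the reduced prescription. The parenthesis naming BID dosing, the addition of two for an evening last dose and the fixed Week 1 figure of 14 all point the other way. A second defence is that BID is the only regimen in Protocol Table 8.a, so measuring against the assigned regimen is a legitimate convention. It could be, but it would measure dose received against dose assigned. SAP 7.7 says it measures adherence to the regimen, and Protocol 7.7 makes one capsule a day an authorised regimen.

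The objections on consequence stand. The summary is descriptive, with no inferential statistics. No compliance threshold defines an analysis set, and dose-adjusted subjects leave the per-protocol set under SAP 7.2 because of the adjustment itself.

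A reader might infer three stronger things that the documents do not support:

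- **That reduced subjects are classed as non-compliant.** SAP 7.7 has no such label or cut-off, and late reductions remain in the 90 to under 110% band.
- **That the table will show worse adherence on lubiprostone.** Reductions under Protocol 7.7 follow adverse events, so an imbalance is plausible, but no reduction rate by arm is given. The nearest figure, in Protocol 4.1.4, is a mean of 1.9 capsules a day in both arms of both US phase 3 studies. It shows no imbalance, but the documents do not say whether reductions were allowed there.
- **That Week 1 compliance is understated in the same way.** It may instead read 100%, as shown in the working.

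**Conclusion.** The point holds for overall capsule-count compliance: the stated rule understates adherence for dose-reduced subjects and conflicts with the SAP's own description of the measure. For an early reduction the understatement is more than a third of the scale (100% reported as 62.5–63.6% from Day 8); from Day 15 it is about a quarter, and it shrinks to a few points near the end of treatment. These figures assume dosing to Day 28, a single reduction taking effect at the start of a day, and no missed or lost capsules. They are effects per subject. The effect on the by-arm table cannot be sized, because the documents give no expected number of reductions. No efficacy result or analysis set is affected. It is worth correcting because the repair is cheap and the table would otherwise mislead.

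**What to change.** In SAP 7.7, define expected capsules as the sum, over dosing days, of the number prescribed under the regimen in force that day: two before the recorded reduction and one from then on. A reduced subject's last day then contributes one capsule; the existing last-day rule stays for unreduced subjects.

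Use the reduction date for every reduction. The time derived in SAP 7.8.1 covers only permanent reductions for an adverse event recorded on the eCRF. Discretionary reductions under Protocol 6.1 are required to be documented in source notes, so their dates need to be captured in the database as well.

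Apply the same denominator to Week 1 and to diary-based overall compliance only together with a rule that an entry recording a dose as not taken does not count as a capsule taken.

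Report the number of dose-reduced subjects by arm beside the compliance table.

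The cost is a short SAP revision, a small programming change and capture of the discretionary reduction dates. The change concerns only how compliance is calculated; it does not touch the dose-reduction rules.

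### SAP 7.7 as written counts recorded missed doses as taken in Week 1, and scores a correctly followed dose reduction as poor compliance

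*SAP*

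**What the plan says.** SAP 7.7 defines compliance as 100 times capsules taken over capsules expected, summarized on the FAS as a continuous variable and in categories (<70%, 70% to <90%, 90% to <110%, >110%).

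**Week 1.** Capsules taken "will be calculated as the number of completed dosing entries in the diary for the first 7 days following randomization", with two records a day anticipated. The denominator is fixed at 14 unless the subject withdraws before completing 7 days.

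**What an entry is.** Later in the same section, under diary compliance, a missed dose is to be ticked 'Not taken', and "therefore there should be 2 entries per day, regardless of actual doses taken". A drug accountability record there is either a time or a 'Not taken' tick.

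**Overall.** Capsules taken is dispensed minus remaining. For the denominator, "The number of capsules expected to be taken is defined as the number of capsules prescribed per day (BID dosing"), multiplied by the days from Day 1 to the last dose date, plus 1 if the last dose was a morning dose or 2 if it was an evening dose. A diary version is also derived, in which "the number of tablets taken is derived from the number of completed entries". If the two disagree, and no comment shows the diary to be right, "the overall compliance calculated using capsule counts will be taken as the correct value". The stated purpose is this: "Overall compliance calculation is considered to indicate compliance with the dosing regimen rather than dosing duration".

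**Dose reduction.** Protocol 7.7 lets the investigator stop either the morning or the evening dose because of an adverse event, and the dose may not go back up. SAP 7.7 makes no adjustment for this.

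**The concern.** There are two separate faults.

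(a) The Week 1 numerator is a count of diary entries, and the SAP itself counts a recorded miss as an entry. On that reading the rate measures diary completion, which the SAP already summarizes separately for Week 1. It also works backwards. Protocol 8.2 asks subjects to note a missed dose in the diary, so one who misses two doses and records them scores 14/14, while one who leaves them blank scores 12/14. The overall rate is protected by the capsule count; Week 1 has no such override.

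(b) The denominator ignores an instructed reduction, although the measure is said to reflect adherence to the regimen. In the overall table a low rate can then mean missed doses or an instruction correctly followed, and the table does not tell them apart.

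Week 1 is the primary-endpoint week, and this is its planned dosing summary. A reader who uses it to judge whether the drug was taken as intended could be misled.

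**Working it through.** **Inputs.** Week 1 expected 14; overall expected 2 × (last dose day − 1) + 1 (morning) or + 2 (evening); category limits 70%, 90% and 110% (all SAP 7.7). Reduction to one capsule a day (protocol 7.7). Treatment to Day 28.

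**The plan's own figure.** 7 days × 2 = 14. The overall formula with a last dose on the evening of Day 7 gives 2 × 6 + 2 = 14. The two agree.

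**(a) Week 1, complete diary, full BID regimen, m missed doses ticked 'Not taken'.** True rate = (14 − m)/14. Rate as written = 14/14 = 100%.

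| m | True rate | True category | Category as written |
|---|---|---|---|
| 1 | 13/14 = 92.9% | 90 to <110% | 90 to <110% |
| 2 | 12/14 = 85.7% | 70 to <90% | 90 to <110% |
| 3 | 11/14 = 78.6% | 70 to <90% | 90 to <110% |
| 4 | 10/14 = 71.4% | 70 to <90% | 90 to <110% |
| 5 | 9/14 = 64.3% | <70% | 90 to <110% |

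One missed dose changes nothing. Two to four are shown one category too high, and five or more two categories too high.

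**(b) Overall, last BID day d, every instructed capsule taken to Day 28.** Taken = 2d + (28 − d) = 28 + d. Expected as written = 2 × 27 + 2 = 56 if the evening dose is kept, or 2 × 27 + 1 = 55 if the morning dose is kept. Expected on the instructed regimen = 28 + d, so the correct rate is always 100%.

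| d | Evening dose kept | Morning dose kept |
|---|---|---|
| 7 | 35/56 = 62.5% | 35/55 = 63.6% |
| 10 | 38/56 = 67.9% | 38/55 = 69.1% |
| 11 | 39/56 = 69.6% | 39/55 = 70.9% |
| 12 | 40/56 = 71.4% | 40/55 = 72.7% |
| 21 | 49/56 = 87.5% | 49/55 = 89.1% |
| 22 | 50/56 = 89.3% | 50/55 = 90.9% |
| 23 | 51/56 = 91.1% | 51/55 = 92.7% |

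A fully adherent subject is therefore placed in <70% when the last BID day is Day 11 or earlier (evening kept) or Day 10 or earlier (morning kept), and in 70% to <90% for Days 12–22 or 11–21.

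**How the two interact in Week 1.** Take a subject reduced from Day 3. Capsules taken = 2 × 2 + 5 = 9. If the stopped doses are ticked 'Not taken', the literal rule gives 14/14 = 100%, which happens to be right. If they are left blank it gives 9/14 = 64.3%. If 'Not taken' entries were excluded and the denominator left at 14, the rate would be 9/14 = 64.3% however the diary was filled in. With both corrections it is 9/9 = 100%.

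**The case against.** On (a), the 'Not taken' sentence belongs to the paragraph on diary completeness, a different measure with its own formula. Elsewhere the diary's dosing item is a date and time of intake (protocol 7.4 and Appendix E), so a programmer deriving capsules taken might well count timed entries only. That reading is available, but the Week 1 rule does not state it, and the only place where SAP 7.7 says what an intake record is includes 'Not taken'. Two competent programmers could produce different tables.

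On (b), protocol 8.1.3 sets the regimen at one capsule twice daily for 4 weeks, and the share of that assigned dose actually received is a coherent quantity. The SAP's contrast between regimen and duration is illustrated by early withdrawal, not by dose reduction, and a prescribed daily number could be read as following the reduced dose. Against this, the explicit BID wording and the fixed 14 point to no adjustment, and a share of the assigned dose is not what the SAP says the rate shows.

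Several limits stand in full. No inferential statistics are planned for compliance; it is not a listed per-protocol criterion and enters no efficacy model. Dose-adjusted subjects are identified elsewhere: they are excluded from the PPS with the reason presented, and dose reduction has its own sensitivity analyses, although the SAP drops the dose-reduction analysis if fewer than 5% of subjects are reduced in the first week. The percentages are per-subject scenarios, not an effect shown on arm-level summaries.

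**Conclusion.** The point holds as a minor one. Following the text of SAP 7.7, Week 1 compliance is 100% for any complete diary, so subjects with two or more recorded missed doses are put in too high a category. Overall compliance for a fully adherent subject reduced after Day 7 is 62.5% or 63.6% instead of 100%. Part (a) rests on the literal reading of a completed entry and on a fully completed diary. Part (b) rests on expected capsules staying at BID, and its figures assume perfect adherence to Day 28. The documents give no counts of missed doses or reductions, so the number of subjects misclassified is unknown. Only descriptive tables are affected; the primary result is not.

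**What to change.** Amend SAP 7.7 before unblinding:

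1. Count as capsules taken only diary dosing entries with a recorded dose time, excluding 'Not taken', both for Week 1 and for the diary-based overall rate.
2. For both Week 1 and overall, set expected capsules at two a day up to the recorded dose reduction and one a day afterwards.

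Make the two changes together: the first alone would lower the Week 1 rate of a subject who was told to stop one dose.

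Optionally, show the number of reduced subjects by arm beside the compliance table. The Visit 3 bottle count can serve as an approximate check on Week 1, but no more, because that visit has a 2-day window.

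The cost is SAP wording and two derivations, using diary times and eCRF reduction records already collected. No procedure changes and the primary analysis is untouched. The one drawback is that reported Week 1 compliance may look lower.

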#### 9.3 Schedule of Observations and Procedures

The schedule for all study-related procedures for all evaluations is shown in Appendix A. Assessments should be completed at the designated visit/time point(s). The recommended visit windows for Visits 2, 3, 4, and 5 are within 2 days of the required visit.

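### SAP 7.7 as worded counts a dose ticked *Not taken* as taken in Week 1 compliance, and the per-protocol dose rule in SAP 7.2 also removes subjects for adjustments made after the Week 1 endpoint

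*SAP*

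**What the plan says.** **Compliance (SAP 7.7).** Compliance is 100 × capsules taken / capsules expected.

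- For Week 1, capsules taken is the "number of completed dosing entries in the diary for the first 7 days following randomization", which should be two per day. Capsules expected is 14 unless the subject withdraws early.
- The paragraph on diary compliance adds: "note that if a dose was missed then 'Not taken' should be ticked", and "therefore there should be 2 entries per day, regardless of actual doses taken". A dosing record there is complete with either a time or a *Not taken* tick.
- Overall compliance is based on "the difference between the total number of capsules dispensed and the total number of capsules remaining at the last visit".
- A second, diary-based overall figure is also calculated, in which "the number of tablets taken is derived from the number of completed entries". If the two differ, then unless a recorded comment supports the diary, "the overall compliance calculated using capsule counts will be taken as the correct value". No such rule is given for Week 1.

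**Per-protocol set (SAP 7.2).** One exclusion is that the randomized dose was adjusted, with no time limit. The same list limits excluded medication to use before the primary endpoint assessment. The PPS is used only for the primary variable, SBM frequency in Week 1. Protocol 13.1.1 lists the dose exclusion in reverse: the dose was *not* adjusted. SAP 7.13 does not mention the change.

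**The concern.** Week 1 is the primary endpoint window, and the Week 1 compliance table is the one summary meant to show whether subjects took the drug during it. If *Not taken* ticks count in the numerator, the table measures diary completion. A subject who records missed doses conscientiously looks fully compliant.

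The PPS rule conditions a Week 1 analysis on events after Week 1. SAP 4.2 allows dose reduction in view of bowel movement frequency and consistency, and Protocol 7.7 allows it for adverse events. Either may relate to response and differ by arm. Removing those subjects can move the PPS estimate although none of their Week 1 data were affected.

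**Working it through.** **1. Week 1 compliance.** Inputs, all from SAP 7.7: denominator 14, two entries per day, a *Not taken* tick being an entry. For a fully completed diary with m missed doses:

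- as worded: 100 × 14/14 = 100% for every m
- counting timed entries only: 100 × (14 − m)/14

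| Missed doses m | As worded | Timed entries only | SAP category (timed) |
|---|---|---|---|
| 1 | 100% | 13/14 = 92.9% | 90 to <110% |
| 2 | 100% | 12/14 = 85.7% | 70 to <90% |
| 4 | 100% | 10/14 = 71.4% | 70 to <90% |
| 5 | 100% | 9/14 = 64.3% | <70% |
| 14 | 100% | 0/14 = 0% | <70% |

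The category is wrong from two missed doses onward.

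**2. Diary-based overall figure.** For 28 days ending with an evening dose, the SAP rule gives 2 × 27 + 2 = 56 expected capsules. Six missed doses give 50/56 = 89.3%, shown as 56/56 = 100%. This figure is normally overridden by the capsule count, so the reported overall value is largely protected.

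**3. Denominator after a dose reduction.** A subject reduced to one capsule a day from Day 4 takes 3 × 2 + 4 × 1 = 10 capsules in Week 1. Counting timed entries against 14 gives 71.4%, although the subject followed the instruction. Correcting the numerator alone would create this second error.

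**4. Timing of dose adjustments.** Protocol Appendix A marks optional dose reduction at the Day 8 and Day 15 visits, although Protocol 7.7 also allows it between visits. Week 1 is the 168 hours from the first dose, so a subject first reduced at Day 15 has a complete Week 1 value and still leaves the PPS. In contrast, the FAS dose-reduction analysis in SAP 7.8.1 drops data only from the time of reduction, and its 5% trigger refers to reductions within the first week.

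**5. Size of the PPS effect (illustration).** The means and SDs come from SAP 6.0: placebo 4 (2.7), lubiprostone 5.9 (4). These reproduce the plan's N. The pooled SD is √((2.7² + 4²)/2) = 3.41; a t-test at 90% power needs 69 per arm; 69 × π/3 = 72.3, so 73 per arm and 146 in total.

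The assumptions are gamma-distributed Week 1 counts rounded to integers, 75 per arm, k lubiprostone subjects removed for reductions after Week 1, and none on placebo. The estimate is the unstratified Hodges–Lehmann shift, the kind obtained by inverting a rank test as SAP 7.8.1 specifies. With k = 0 it is about 1.5.

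| Who is removed | k = 2 | k = 4 | k = 8 |
|---|---|---|---|
| At random | 1.5 | 1.5 | 1.5 |
| Chance proportional to frequency | 1.4 | 1.4 | 1.3 |
| Highest frequencies | 1.3 to 1.4 | 1.2 | 1.0 |

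On the mean scale the last row would be about 1.6, 1.3 and 0.9, down from 1.9. That overstates the change for a rank-based analysis.

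The loss of precision is small. If 2%, 5%, 10% or 20% of both arms were removed (3, 7.5, 15 or 30 of 150), approximate PPS power would be 91%, 90%, 88% or 85%, before other exclusions.

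**The case against.** On compliance, the strongest reply is intent. The quantity is called capsules taken, and the sentence about *Not taken* stands in the paragraph on diary compliance. Counting ticks would make Week 1 drug compliance largely repeat Week 1 diary compliance. The rule that a comment may show the diary to be right over the capsule count makes sense only if the diary counts doses taken. This is persuasive about what was meant. It does not supply the missing words: both paragraphs rely on two entries per day, and the only text explaining that count includes missed doses.

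Sites also document accountability at Day 8. That does not give a Week 1 fallback: the SAP does not use it, and Protocol 9.3 says "The recommended visit windows for Visits 2, 3, 4, and 5 are within 2 days of the required visit", so the count need not match Days 1 to 7.

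On the PPS, excluding anyone whose dose was adjusted is one possible definition of a per-protocol set. The FAS analysis already examines dose reduction, and major-deviation criteria are still to be defined before unblinding. All of this stands, so the bullet is over-broad rather than contradictory within the SAP. Blinded review and signed exclusion reasons make the exclusions visible but do not narrow the rule.

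Both outputs are secondary in any case. The compliance table is descriptive, compliance is not a PPS criterion, and the PPS analysis is supportive.

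**Conclusion.** Both parts hold as points of wording and definition, and both are minor. As written, Week 1 compliance cannot show missed doses in a subject who completes the diary, and the PPS can lose valid Week 1 data because of later events. The compliance figures are exact for a fully completed diary. The PPS figures rest on an assumed distribution, assumed numbers removed and one-sided removal; the documents give no reduction rate.

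Three stronger readings are not supported:

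- A reader might infer that missed doses *will* be reported as taken. The text permits that derivation but does not show that it would be programmed so, and intakes were probably meant.
- A reader might infer that overall compliance is equally affected. Capsule counts normally prevail there.
- A reader might infer that the efficacy conclusion is at risk. The primary FAS analysis and N = 146 do not depend on either rule. In the illustration, removal tied to frequency moves the PPS estimate toward no effect; the direction in practice is unknown.

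**What to change.** **SAP 7.7.** Define diary-based capsules taken, for Week 1 and overall, as the number of dosing entries with a recorded intake time, with *Not taken* counting as 0. State how expected capsules are counted from the date of a recorded dose reduction, so that a subject following a permitted reduction is not shown as non-compliant. A Visit 3 capsule-count check is not proposed, because of the visit window.

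**SAP 7.2.** Limit the dose bullet to adjustments made before the end of Week 1 (168 hours after the first dose). Reconcile it with the reversed bullet in Protocol 13.1.1 and record the change in SAP 7.13.

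**Clerical, also SAP 7.2.** Write SBM rather than BM in the three-or-more-per-week bullet, as in Protocol 7.2 and 13.1.1. Word the loose-stool bullet as a failure to meet the criterion.

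**Cost.** These are wording edits before unblinding, with no new data collection intended. The diary already separates a time from *Not taken*, and Protocol 7.7 puts dose reductions in the eCRF. Protocol 6.1 mentions only source notes for reductions based on bowel response, so confirm that those dates also reach the eCRF. Correcting the protocol bullet itself would follow the usual protocol change process.
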